## I. ABBREVIATIONS

ARDS	Acute respiratory distress syndrome
AT	As-treated censoring approach
CED	Cohort entry date
CPT	Current procedural terminology
CSI	Corticosteroids of interest (DEX, hydrocortisone, Methylprednisolone, Prednisone)
DEX	Dexamethasone
ECMO	Extracorporeal membrane oxygenation
EHR	Electronic health records
FDA	US Food and Drug Administration
HCPCS	Healthcare common procedure coding system
HCRU	Healthcare resource utilization
ICD	International classification of disease
IMV	Invasive mechanical ventilation
IT	Initial treatment censoring approach
KRT	Kidney replacement therapy
MPRED	Methylprednisolone
mWHO	Modified World Health Organization severity score
NAAT	Nucleic Acid Amplification Test
NDC	National drug code
NIV	Non-invasive ventilation
O2	Oxygen
PS	Propensity score
RCA	Research collaboration agreement
RWD	Real-world data
RSS	Risk set sampling
SA	Sensitivity analysis
SES	Socioeconomic status
WHO	World Health Organization

## II. BACKGROUND

### A. Emergence of COVID-19 and treatment

As of May 25, 2021, there have been over *32.7 million cases* of COVID-19 in the United States (US) since the emergence of SARS-CoV-2 in late 2019 [**WHO 2020(a)**]. COVID-related hospitalizations are at an estimated cumulative rate of *553.8 per 100,000* in the US population, with COVID-19 related deaths in the US reaching over *587,000* [**CDC 2020**]. Despite the availability of vaccines across the US, the burden of disease remains high and determining the effectiveness of potential COVID-19 therapeutics continues to be an urgent concern.

On June 22, 2020, the RECOVERY Collaborative Group published preliminary findings demonstrating a significant reduction in 28-day mortality among hospitalized COVID-19 patients in the UK treated with the corticosteroid dexamethasone (DEX) [**RECOVERY 2020**]. As a result of this trial, the NIH Treatment Guidelines Panel updated their guidelines to recommend use of DEX in hospitalized patients receiving supplemental oxygen (O2) therapy or mechanical ventilation and the World Health Organization (WHO) updated their guidelines to recommend DEX in severe and critically ill hospitalized patients [**NIH 2020(a); WHO 2020(b)**]. In early February 2020, results from the DEXA-ARDS trial among patients in Spain in intensive

care units (ICUs) with established moderate-to-severe acute respiratory distress syndrome (ARDS) and invasive mechanical ventilation (IMV), which occurs among patients with severe COVID-19, reported a decrease in 60-day mortality for patients randomized to intravenous DEX compared to continued routine intensive care [21% (29/139) vs. 36% (50 /138)] [*Villar 2020*]. However, since the trial was stopped by the data safety monitoring board due to low enrollment rate, we focus here on the RECOVERY trial, but have incorporated a sensitivity analysis to align with the mortality endpoint used in the DEXA-ARDS trial [see *section VII. Sensitivity Analyses, S45*].

## **B. Randomized Evaluation of COVID-19 Therapy (RECOVERY): Efficacy of dexamethasone**

The RECOVERY trial, which first reported preliminary results on June 22, 2020, was an open-label, 1:2 randomized controlled trial of 6,425 patients randomized to either 6 mg of DEX daily for 10 days (n = 2,104) or usual care (n = 4,321). Overall, 22.9% of patients assigned to the DEX group died within 28 days of randomization vs. 25.7% of the control arm (rate ratio [RR] of 0.83, 95% CI [0.75, 0.93]). The difference in survival between the two groups varied noticeably when stratified by baseline COVID-19 severity level. While the incidence of death was lower in the DEX group, compared to the usual care group, among patients receiving IMV (RR: 0.64, 95% CI [0.51, 0.81]) and among those receiving supplemental O2 therapy but not IMV (RR: 0.82, 95% CI [0.72, 0.94]), there was no discernable difference among patients who were not receiving any supplemental O2 (RR: 1.19, 95% CI [0.91 to 1.55]) [*RECOVERY 2020*].

The effectiveness of DEX in preventing death among moderate to severe COVID-19 patients has not yet been confirmed or established in routine care, yet DEX utilization has substantially increased in the US since June 2020 [*Action 2021*]. Thus, to evaluate the effectiveness of DEX in preventing death under routine use in a timely manner, we sought to conduct an observational cohort study using US-based real-world data (RWD).

[figure not shown]
In one of the explorations conducted prior to the finalization of this protocol [see *Appendix A.2. Exploration 2*], we compared the distribution of key patient characteristics between a version of our hospitalized US-based RWD study cohort to those reported for the hospitalized UK-based patients randomized in the RECOVERY trial. The RECOVERY trial was a large, pragmatic randomized trial that simplified the data collection process in an effort to minimize the already heavy burden of the pandemic on frontline workers. Exploration of baseline clinical differences between the real-world study and trial populations was therefore limited by the degree of available information for the trial patients. However, among the available RECOVERY trial data, we identified important clinical and demographic differences in the trial population versus this study's populations at baseline.

**C. Action Research Collaboration Agreement (RCA) with the US Food and Drug Administration (FDA)**

Action entered a research collaboration agreement (RCA) with the US Food and Drug Administration (FDA) to use RWD to advance the understanding and the natural history of COVID-19 in specific patient populations, as well as treatment and diagnostic patterns during the coronavirus disease (COVID-19) pandemic. Action is collaborating with the FDA to identify and analyze fit-for-purpose data sources (i.e., near-real-time information, meaningful population size, and sufficient capture of key study parameters and longitudinal patient experience [Gatto 2019; FDA 2018]) to characterize COVID-19 patient populations, identify risk factors for COVID-19-related complications, and contribute to the scientific evaluation of potential interventions.

We are using a stepwise approach to conduct this research, separating the research process into three distinct sequential phases: *Exploratory* (data explorations done in advance to facilitate key design decisions, as noted above), *Diagnostic* (requirements that must be satisfied prior to viewing treatment-specific outcomes, e.g., sample size and covariate balance), and *Inferential* (final comparative analyses) [see Figure 1 below].

Figure 1. RWD Research Process phase schematic

In the *Exploratory Phase*, the Action research team engaged with the FDA RCA team to better understand the data and make decisions about the study design to inform the development of this protocol. The following explorations, which are further detailed in *Appendix A*, were completed prior to protocol finalization:

1. **Exploration 1:** Defining a COVID-19 study population
2. **Exploration 2:** Comparison of our study cohort and design to the RECOVERY trial
3. **Exploration 3:** Defining the time period for measuring a modified version of the COVID-19 severity score published by the World Health Organization (mWHO score) at treatment index
4. **Exploration 4:** Determining the definitions for mWHO COVID-19 severity components
5. **Exploration 5:** Determining the cohort entry date truncation

Given the periodic data updates during the *Exploratory Phase*, explorations were carried out on earlier cuts of the data. Therefore, although the cohort design remained relatively consistent across explorations, the cohort samples used for each exploration differed from each other, and from the final cohort that will be used for the diagnostic and inferential phases of the analysis [See *IV. Data Source*].

For the *Diagnostic Phase*, we developed a checklist of diagnostic criteria [see *section VI.B, Table 4*] that must be satisfactorily completed prior to beginning the implementation of the *Inferential Phase*. As such, the relationship between the treatment and outcome of interest will not be described or evaluated in the analytic dataset until we reach consensus that the diagnostic criteria are satisfied. Upon each data update, the Diagnostic results will be presented to the FDA RCA team until there is consensus that we have satisfied the necessary criteria to progress to the *Inferential Phase* [see *section VI.C*].

### III. RESEARCH AIM AND OBJECTIVES

As part of the RCA with the FDA, this study informs the overall project to establish a system for rapid-cycle evaluation, using best practice scientific and operational methods, as applied to relevant and meaningful clinical questions. In this study, we seek to assess the effectiveness of DEX to reduce the risk of inpatient mortality within 28 days among US patients hospitalized with COVID-19 diagnosis or SARS-CoV-2 infection, overall and stratified by COVID-19 severity subgroups [defined according to the presence of encounters indicating supplemental oxygen or ventilation; see *section V.D* for additional subgroup detail], using the HealthVerity database.

The principles outlined by Hernan et al. emphasize the importance of explicitly emulating a hypothetical target trial when planning a RWD analysis to yield RWE [Hernan, Robins 2016; Hernan, Sauer 2016]. Although we reference the UK RECOVERY trial as a basis for comparison [RECOVERY 2020], we sought to emulate a hypothetical target trial with varied design elements, and research questions tailored for US practice and US patients. In a sensitivity analysis, we further sought to replicate the RECOVERY trial design elements (to the extent possible) [see *section VII. Sensitivity Analyses, SA8*].

Specifically, among US patients hospitalized with COVID-19 diagnosis or SARS-CoV-2 infection without prior use of any corticosteroid of interest (CSI; DEX, methylprednisolone, prednisone, hydrocortisone) estimate the hazard ratio and corresponding 95% confidence interval for the risk of inpatient mortality within 28 days after treatment initiation, comparing *new use of DEX* with:

- *non-users of corticosteroids (Primary objective I; DEX+ vs. CSI-)*, to evaluate the potential benefit of DEX above ‘standard of care’ inpatient treatment for COVID-19, where ‘standard of care’ excludes all CSIs (DEX, MPRED, PRED, HC).
- *non-users of DEX (Secondary objective I; DEX+ vs. DEX-)*, to evaluate the potential benefit of DEX above ‘standard of care’ inpatient treatment for COVID-19, where ‘standard of care’ excludes DEX but may include those newly treated with a non-DEX CSI (MPRED, PRED, HC). This comparison is most similar to the RECOVERY trial that compared DEX to ‘standard of care’ [RECOVERY 2020].
- *methylprednisolone active comparator (Secondary objective II; DEX+ vs. MPRED+)*, to evaluate the potential benefit of DEX compared to a clinically meaningful treatment alternative (here, another corticosteroid), among patients without prior use of DEX or MPRED (traditional new user design). This comparison excludes those treated with a CSI other than DEX and MPRED.

Under the assumption that all of the CSIs are protective [NIH 2020(c)], we would expect a stronger effect for CSI- comparison (**Primary objective**), some protective effect for the DEX- comparison (**Secondary objective I**), and little or no effect for the MPRED+ comparison (**Secondary objective II**).

**Key subgroups:**

Findings will be presented for *DEX versus* each of the 3 referent groups (*CSI-*, *DEX-*, *MPRED+*) among each of the following subgroups of patients to evaluate the potential benefit of DEX compared to ‘standard of care’ or a clinically meaningful treatment alternative stratified by COVID-19 disease severity at the time of treatment index [defined according to the presence of encounters indicating oxygen or ventilation; see *section V.D* for additional subgroup detail]:

- (1) no O2;
- (2) any O2 or non-invasive ventilation (O2/NIV);
- (3) any IMV; and
- (4) composite of O2/NIV/IMV.

*Table 1. Summary of comparisons and populations of interest for each objective*

Objective	Exposure	Referent Group	Population(s) of interest
Primary	DEX+	CSI-	Overall
Secondary-I		DEX-	
Secondary-II		MPRED+	
Key subgroups		CSI-	Each of the following subsets of patients: (1) no O2; (2) O2/NIV; (3) IMV; and (4) composite O2/NIV/IMV
	DEX-		
	MPRED+		

**IV. DATA SOURCE**

This study uses de-identified RWD from HealthVerity comprising open and closed Medical claims and includes major payer types (commercial and federal Medicaid and Medicare programs) from all US states and territories, open and closed Medical and Outpatient Pharmacy claims, Laboratory Data including results, and Hospital Chargemaster transactional records that include diagnoses, procedures and treatments for billable inpatient and outpatient hospital encounters. The data elements derived from chargemaster data are listed in Appendix C along with their percent missingness. The database also includes clinical observations as recorded in electronic health records (EHR), where available. The open claims are sourced in near-real-time from practice management systems, billing systems and claims clearinghouses, and the closed claims are sourced from insurance providers and payers. All ages are included in the full database with ages 65 or older over-sampled to account for the under-representation of Medicare aged patients with commercial coverage. The HealthVerity Medical Claims, Pharmacy, Laboratory and Hospital Chargemaster dataset has been used for scientific publications of COVID-19 research [*Burn 2020; Gordon 2020; Harvey 2021; Murk 2020*].

As of **12-March-2021**, the data spans the time period *01-December-2018* to **22-February-2021** (the last date of available data) and included **58,233,249** patients. The data will be updated periodically as new data become available until we are able to achieve sufficient sample size, as defined in the diagnostic checklist of the statistical analysis [see *section VI.B*].

The primary endpoint of 28-day mortality is defined using Inpatient Chargemaster claims with a discharge status of ‘expired’ indicating death. Given that the HealthVerity data source is relatively new, there are no validation studies of this data source yet for mortality or other endpoints. However, use of discharge status to determine mortality endpoints among hospitalized

COVID-19 patients has been used in both in a similar chargemaster data source [*Rosenthal 2020*] and for national surveillance reporting [*CDC-NCHS 2021*].

We further explored the data given the importance of this variable to our study. When we compared use of discharge status of death to the separate data files from the vendor providing month of death (date of death was redacted for privacy concerns), we found that all patients with a death month indicated also met our endpoint definition. Further, when we compared weekly deaths over time in our overall cohort of patients hospitalized with COVID-19 (reminder that we will not look at death stratified by treatment until after the diagnostic phase is completed), we identified similar trends to that of two external national benchmarks, the Centers for Disease Control {*CDC-NCHS 2021*} and data sourced from State and local health agencies {*NYT 2021*}, providing further assurance of the accuracy of the capture of our endpoint.

## V. STUDY DESIGN

[figure not shown]
Key elements of the study design are described in the text below and additional measure definition detail is available upon request.

### A. Study design

This study is an observational cohort study using secondary healthcare data. The study diagram and its components are illustrated and further detailed below [*see Figure 2*].

Figure 2. Study diagram

Inclusion/Exclusion Criteria	
COVID-19 confirmation	Hospitalized patients with confirmed COVID-19 (ICD 10 diagnosis: U07.1 or positive or presumptive positive SARS-CoV-2 diagnostic laboratory test result; Day -21 to Day T).
Baseline Exclusion	Exclude patients without activity in the 183 day baseline period (Day -183 to Day -1).
Missing Demographics Exclusion	Exclude patients with missing age, sex, or region on the hospital admission date (Day 0; CED).
COVID-19 Vaccine Exclusion	Exclude patients with any record of a COVID-19 vaccine on or any time prior to the treatment index date given that these patients are assumed to be selectively different (Day S to Day -1).
Treatment Exposure	Hospitalized COVID-19 patients with new use of systemic dexamethasone (DEX+) or referent groups (CSI-, DEX-, MPRED+). Treatment index date (Day T) must occur between hospital admission date (Day 0; CED) and 1 day prior to hospital discharge date (Day D-1).
Treatment Washout	Exclude patients with prior systemic CSI use from all comparisons (Day -90 to Day T-1).
Covariate Assessment	
Baseline	Baseline (pre-admission) comorbidities, co-medications, and healthcare resource utilization (HCRU; Day -183 to Day -1).
Pre-admission	COVID-19-related symptoms, complications, and HCRU leading up to the hospital admission date (Day -21 to Day -1).
On admission	Demographics, facility characteristics, and covariates related to admitting status (Day 0; CED).
Pre-treatment (Inclusive)	Treatments administered prior to or concurrent with treatment index date, pre-treatment clinical status, and time from admission to treatment (Day 0 to Day T).
mWHO Severity	COVID-19 severity per modified version of WHO ordinal scale (mWHO), used for matching and subgrouping of DEX+ and referent patients (Day T-1 to Day T).
Outcome Assessment	
Follow-up	Follow-up window for primary outcome of 28-day inpatient mortality (Day T+1 to the earlier of Day T+28 or D).

*CED, Cohort Entry Date; D, Hospital discharge date; S, Start of available data; T, Treatment index date*

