### **E. Primary outcome definition and follow-up (28-day mortality)**

The primary outcome will be inpatient mortality over a 28-day period, sourced from the chargemaster discharge status field. In the primary analysis, follow-up will begin 1 day after treatment index (*Day T+1*) and will continue until the earliest occurrence of the mortality endpoint, 28 days of follow-up reached (*Day T+28*) or discharge from hospital (*Day D*). This approach, referred to here as the “initial-treatment” (IT) approach, assumes patients continue the initial treatment without censoring upon treatment changes, similar to the intent-to-treat approach used in the RECOVERY trial and other randomized controlled trials.

We will also implement an as-treated (AT) censoring approach that additionally censors upon treatment changes. For the DEX+ versus CSI- comparison (**Primary Objective**), this will censor the follow-up of non-users of CSI upon start of any CSI use. For the DEX+ versus DEX- comparison (**Secondary Objective I**), this will censor the follow-up of non-users of DEX upon start of any DEX use. For the DEX+ vs. MPRED+ comparison (**Secondary Objective II**), this will censor the follow-up of patients who start DEX use upon start of any MPRED use and the follow-up of patients who start MPRED use upon start of any DEX use.

A sensitivity analysis will also broaden the follow-up period for capturing inpatient mortality to consider deaths within 60 days after treatment index (T+60) if they occur during the index hospitalization. [see section VII. SENSITIVITY ANALYSES, SA5].

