**C. Inferential phase**

The *Inferential Phase* begins after all diagnostic criteria are satisfied or the protocol is publicly posted, whichever is later. To prevent changes to the underlying patient or event-level data from occurring when new data are available, the data cut will be locked at the start of the *Inferential Phase*.

For the primary outcome of 28-day mortality, the following will be reported in the overall cohort and within each subgroup of interest before PS matching and after PS matching:

- Rates reported per 1,000 person-days, overall and for each subgroup.
- Hazard ratios (HR) and corresponding 95% CIs for the effect of DEX+ compared to each referent (CSI-; DEX-; MPRED+) overall and for each subgroup using PS-matched cohorts. If residual imbalance ( $0.10 \leq ASD \leq 0.15$ ) remains after PS matching, Cox proportional hazard models may be specified to adjust for any imbalanced confounders. Otherwise, HRs will be unadjusted.

In subgroups that do not achieve the minimum sample size requirements, results will be presented in the context of an estimation framework rather than a formal hypothesis testing framework, and findings should be interpreted with caution.

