	SA4: Broaden patient population to include patients with confirmed COVID after treatment index*	
Detail: Additionally include patients with positive or presumed positive lab values or COVID-19 diagnosis occurring anytime during hospitalization, including discharge diagnoses.
 
Purpose: Evaluate whether HR is robust within a broader cohort including people without a COVID-19 diagnosis prior to or at admission. Will increase the sample size by approximately 10%, but may have the potential for misclassification of patients who were hospitalized for reasons other than COVID-19 who had a secondary diagnosis of COVID-19 or contracted COVID-19 during hospitalization as patients hospitalized for COVID-19.

Category	Brief Description	Detail / Purpose
Follow up censoring	SA5: Broaden the follow-up period for capturing inpatient mortality endpoints*	
Detail: Determine whether treatment with DEX reduces the risk of inpatient mortality within 60 days during the initial hospitalization.
 
Purpose: Evaluate effect of DEX on risk of inpatient death over a longer time frame. Aligns with mortality endpoint definition used in dexamethasone-ARDS trial [Villar 2020].

Additional subgroup	SA6: Stratify by ICU at Treatment index	
Detail: Estimate HR within ICU subgroup, defined based on the presence of a medical encounter with a revenue or department code indicating ICU at treatment index.
 
Purpose: Evaluate whether patients who initiate treatment while in the ICU differ from those who do not (within the overall cohort), an alternative proxy for COVID-19 severity.

Alternative subgroup definition	SA7: Define COVID-19 severity based on procedures alone	
Detail: Estimate HR within each of the mWHO subgroups using an algorithm that relies on procedural encounters only for defining O2/NIV and IMV (without the additional diagnostic encounters included in the primary definitions).
 
Purpose: Evaluate the impact of the robustness of findings among patients identified as O2/NIV and IMV and those identified as having neither (no O2) and understand the impact of the shift from lower to higher COVID-19 severity on the effect of DEX+ on 28-day mortality.

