**Summary of key findings:** Within our hospitalized COVID-19 cohorts, for patients in the data cut received 22-February-2021, the latest hospital admission was 07-February-2021 and the median LOS was 6 days. We see a data lag of ~15-20 days between the latest available admission date and the day of data receipt, which was also seen via other data cuts. Considering a data lag of 20 days and the 95th percentile of 27 days LOS, we assume the end of the study period should be a minimum of 47 days prior to the end of the data to account for at least 95% of the observed hospital stays [see *Figure A.6*].

In the weekly LOS plots comparing an older data cut from 16-November-2020 to a newer data cut from 22-February-2021, we began to see the lines diverge the week of 17-September-2020, approximately 60 days before the latest

admission date observed within the data cut received 16-November-2020. [see Figure A.7]

For each data cut, the number of monthly admissions drops quickly, and likely artificially, as the cohort entry date approaches the data cutoff [see Figure A.8]. Death events also drop quickly, and likely artificially, as the cohort entry date approaches the data cutoff [see Figure A.9]. For both admissions and deaths, data from the more recent data cuts converge with data from earlier data cuts approximately 60 days prior to the data cutoff.

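### Follow-up stops at discharge, so the primary hazard ratio is cause-specific for death in hospital, and no 28-day risk contrast is planned for the 28-day risk the protocol targets

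*Protocol*

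**What the plan says.** Section III (Research aim and objectives) seeks to "assess the effectiveness of DEX to reduce the risk of inpatient mortality within 28 days among US patients hospitalized". It then names a hazard ratio as the effect measure and words it as being for that 28-day risk. The sample-size item in Table 4 likewise pairs a hazard ratio of 0.8 with a baseline 28-day mortality risk.

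Section V.E defines the endpoint: "The primary outcome will be inpatient mortality over a 28-day period, sourced from the chargemaster discharge status field". Follow-up starts on Day T+1 and "will continue until the earliest occurrence of the mortality endpoint, 28 days of follow-up reached", or discharge if that comes first. Figure 2 gives the same rule: "Follow-up window for primary outcome of 28-day inpatient mortality (Day T+1 to the earlier of Day T+28 or D"). Table A.1 in Appendix A repeats it.

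Section VI.C lists two results for the primary outcome: "Rates reported per 1,000 person-days, overall and for each subgroup", and "Hazard ratios (HR) and corresponding 95% CIs for the effect of DEX+ compared to each referent".

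SA5 lengthens the window but not beyond the index stay: "Determine whether treatment with DEX reduces the risk of inpatient mortality within 60 days during the initial hospitalization".

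Neither SA1 to SA8 nor the limitations in section VIII mention live discharge as a competing event.

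**The concern.** Ending follow-up at live discharge removes the patient from the risk set. The hazard ratio then compares death rates among patients still in hospital. The probability of dying in hospital by Day T+28 depends on that hazard and also on how quickly patients leave alive: a longer stay means longer exposure to the risk of an inpatient death.

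If dexamethasone changes time to discharge, the hazard ratio and the 28-day risk contrast can differ in size, or even in direction, while readers would take the hazard ratio as the effect on 28-day inpatient mortality risk. Discharge is not a minor event here. With a 6-day median stay, most patients leave the risk set well before day 28, and mostly alive at the mortality risks considered below.

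**Working it through.** The protocol gives no event count and no risk by arm, so there is no stated figure to reproduce. The check asks how far the two measures can separate.

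**Inputs from the protocol**
- Median stay 6 days: "the latest hospital admission was 07-February-2021 and the median LOS was 6 days" (Appendix A, Exploration 5). The same exploration gives a 95th percentile of 27 days.
- Hazard ratio 0.8, 80% power, two-sided 0.05 (Table 4).
- Highest referent 28-day risk considered: 25.7%, the control-arm risk of the reference trial (section II.B).

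**Assumptions**
- Constant cause-specific hazards d (death) and r (live discharge).
- Referent 28-day inpatient risk 15% (range 10% to 25.7%).
- Dexamethasone discharge hazard 10% or 20% lower or higher than the referent. These shifts are scenarios, not protocol figures.

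**Model.** 28-day risk = d/(d+r) × [1 − exp(−28(d+r))].

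**Calibration.** d + r = ln 2/6 = 0.1155 per day. Solving for a 15% risk gives d = 0.0180 and r = 0.0975. Check: 0.0180/0.1155 × (1 − 0.0394) = 0.150. The implied 95th percentile of stay is ln 20/0.1155 = 25.9 days against the stated 27, so the approximation is fair.

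**A. Equal 28-day risks (15% in both arms): what hazard ratio results?** Multiply r by the shift and solve for the dexamethasone d that returns 15%.

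| Discharge hazard, DEX vs referent | DEX death hazard | Hazard ratio |
|---|---|---|
| −20% | 0.0151 | 0.84 |
| −10% | 0.0165 | 0.92 |
| equal | 0.0180 | 1.00 |
| +10% | 0.0196 | 1.09 |
| +20% | 0.0212 | 1.17 |

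Over median stays of 4 to 10 days and referent risks of 10% to 25.7%, the 20% shifts give hazard ratios of 0.81 to 0.89 (lower discharge) or 1.12 to 1.19 (higher discharge).

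**B. Fixed hazard ratio: what 28-day risk ratio results?**

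| Hazard ratio | Discharge −20% | equal | +20% |
|---|---|---|---|
| 1.00 | 1.17 | 1.00 | 0.87 |
| 0.90 | 1.07 | 0.91 | 0.79 |
| 0.80 | 0.96 | 0.82 | 0.71 |

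The middle row shows a reversal: a hazard ratio of 0.90 sits beside a risk ratio of 1.07 when discharge is 20% slower.

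**C. Consequence at the planned precision.** Deaths for hazard ratio 0.8 at 1:1 matching = 4 × (1.96 + 0.84)²/(ln 0.8)² ≈ 631, so SE(log HR) = 2/√631 = 0.080.
- Equal 28-day risks, discharge −20%: ln 0.836/0.080 ≈ −2.26, so the 95% CI lies below 1 in about 62% of studies.
- Equal 28-day risks, discharge +20%: the CI lies above 1 in about 52%.
- True 28-day risk ratio 0.80, discharge +20%: hazard ratio 0.91, power about 22%. With equal discharge: hazard ratio 0.78, power about 89%.

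These are not false-positive rates or power lost to a faulty test. In each case the hazard ratio correctly estimates its own target. The figures show how often its conclusion would differ from one about 28-day risk.

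**Simulation of the same model** (100,000 per arm, discharge −20%, equal risks): 28-day risk 15.1% in both arms. The Cox hazard ratio is 0.83 with follow-up stopped at discharge and 0.99 with discharged patients kept event-free to day 28.

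**The case against.** The strongest reply is that the protocol is open about its choice. Section III names a hazard ratio, the endpoint is consistently called inpatient mortality, and a cause-specific hazard ratio is a legitimate estimate. The follow-up rule also resembles the reference trial's as described in Table A.1. Competing-event methods are often left to an analysis plan, and section VI.C does not say its list is exhaustive. No document gives a discharge difference by arm, and the 6-day median runs from admission rather than Day T and includes stays ending in death. Finally, a cumulative-incidence contrast has its own dependence on discharge, because deaths after discharge are not captured.

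Much of this stands. The hazard ratio should be kept, the size of any gap is unknown, and the added contrast is a complement. At the design hazard ratio of 0.80, shifts of up to 20% in discharge leave the risk ratio below 1, so reversal needs a hazard ratio nearer 1.

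It does not remove the mismatch. The protocol itself fixes the follow-up rule and the reported measures, and it presents the hazard ratio as the effect on a 28-day risk without stating the condition under which that holds.

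**Conclusion.** The concern holds, and the protocol should be changed. As written, the primary estimate is a cause-specific hazard ratio for death in hospital, while the stated aim is a 28-day risk of inpatient death. SA5 carries the same gap to day 60.

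For discharge hazards differing by 20%, the gap is enough to turn equal risks into a hazard ratio of 0.84 or 1.17, or equal death hazards into a risk ratio of 1.17 or 0.87. These sizes rest on constant hazards, the 6-day median, the assumed 15% referent risk and the assumed shifts. The direction in this study cannot be predicted from the protocol. That the two measures can differ does not depend on those particular values. The existing estimate is not invalid; it does not by itself answer the stated question.

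**What to change.** Amend sections V.E and VI.C, and apply the same to day 60 in SA5:

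1. For the initial-treatment analysis, count patients discharged alive as free of inpatient death to Day T+28. Report the Aalen-Johansen 28-day cumulative incidence by arm, with risk ratio and risk difference, as the estimate of 28-day inpatient mortality risk. Add a subdistribution hazard ratio if a hazard-scale summary of that risk is wanted. One minus Kaplan-Meier with discharge censored would not serve: in the model above it gives 1 − exp(−28 × 0.0180) ≈ 40% where the true risk is 15%.
2. Keep the hazard ratio and person-day rates, labelled as cause-specific.
3. Report the discharge hazard by arm, so that readers can see whether a result comes from deaths, discharges or both.
4. For the as-treated analysis, which also censors at treatment change, use Aalen-Johansen or a weighted subdistribution model. Moving discharge times to day 28 is not enough there.

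The cost is wording and one added analysis on dates and discharge status already held. It can be specified before any treatment-specific outcome is seen. The downside is that deaths after discharge stay uncounted. If one arm leaves earlier and some of those patients then die, the 28-day contrast would favour that arm. It must be read as inpatient mortality only, and section VIII should say so.
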